When interested patients arrive at the clinic, the CRC or RA will obtain their written informed consent. The trained recruiter will provide a detailed description of the voluntary nature of participation, study procedures, risks and potential benefits. The potential participant will be provided the opportunity to ask questions and review the consent information with family and friends prior to making a decision to participate. Participants will be told that they do not have to answer any questions if they do not wish and can drop out of the study at any time, without affecting their medical care or the cost of their care, or that of their spouse or partner. They will be told that they may not benefit directly from the study and that all information will be kept strictly confidential, except as required by law. All participants will be given a copy of the signed informed consent form. For participants who are offered the opportunity to participate in a qualitative interview, and elect to do so, we will repeat the above procedures with an interview-specific additional consent document. Participants will have the opportunity to discuss the consent document with research personnel, and will be informed about the voluntary nature of participation in the interview. Participants will receive a signed copy of the additional consent documentation. We additionally have proposed to conduct qualitative interviews with the 2 Community Health Workers serving patients within this study. We will consent these Penn Medicine staff members using the attached consent form. Due to COVID-19 we have requested a waiver of written documentation of consent, due to the significant challenges posed by obtaining documentation of consent given pandemic precautions limiting in-person visits, and the limited access to technology among our study population.

Children and Adolescents

Not applicable

Adult Subjects Not Competent to Give Consent

Competence will be assessed by the interviewer and we will exclude patients who cannot or will not give consent.

2. Waiver of Consent

Waiver or Alteration of Informed Consent*

Waiver of written documentation of informed consent: the research presents no more than minimal risk of harm to subjects and involves no procedures for which written consent is normally required outside of the research context

Minimal Risk*

Impact on Subject Rights and Welfare*

Waiver Essential to Research*

Additional Information to Subjects

Written Statement of Research*

No

If no written statement will be provided, please provide justification

Due to the current COVID-19 pandemic, we are unable to meet study participants in-person, therefore prohibiting us from sharing a physical copy of the written statement of research. However, all

participants consenting to participate in qualitative interviews who were previously enrolled as participants in the Engage RCT were previously provided with a physical copy of the overall study consent form, which explains the overall goals of the research project, and refers to the qualitative interview process.

The following documents are currently attached to this item:

There are no documents attached for this item.

Risk / Benefit

Potential Study Risks

A potential risk of this study is a breach of participant confidentiality. We will minimize this risk by linking individual identifying information with participant ID numbers only in one single secure file. Due to the financial incentives in this study, we will be collecting social security numbers so that we can complete W-9 forms for participants. Social security numbers only will be used to generate W-9 forms and will be deleted once they are no longer needed. We will also collect home addresses to mail incentive payments. This will be done through a University of Pennsylvania approved partnership with Greenphire ClinCard. Accidental disclosure of social security numbers could lead to identity theft. We will use commercial-grade encryption to protect social security information in transit. Names and addresses will be stored in encrypted databases. These data will be viewable only by the respective participants and the study coordinator. All other members of the research team will be able to view only participant ID numbers. There will be no functionality in the web application to export a dataset with identifiable information. Even the study arms will be identified by code letters until both the statistician and PI agree that analysis is complete.

Potential Study Benefits

Participants may benefit by improving control of their diabetes through increased self-monitoring of their blood glucose level.

Alternatives to Participation (optional)

Data and Safety Monitoring

Data will be monitored by the Principle Investigator and other investigators throughout the data collection and analysis process. We will have an internal safety review that is blinded to arm and a quarterly discussion of adverse events. We will ask patients about any medical incidents and hospitalizations at the 3 and 6 month follow up visits and record their responses. A nurse practitioner will then determine if medical incidents and hospitalizations are study related. Study related events will be discussed with our internal DSMB.

The following documents are currently attached to this item:

There are no documents attached for this item.

Risk / Benefit Assessment

There is a very low ratio of risk to benefit in this study. There is minimal risk to participation in the study.

General Attachments

The following documents are currently attached to this item:

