A trial of a hybrid DFI/CHW intervention that incorporates strategies for coping with failure among a population of low-income patients with diabetes. Diabetes is an ideal condition in which to test this innovative intervention; the challenges of carrying out healthy behaviors for patients with diabetes have been well described. In addition, the enormous public health and economic challenge of diabetes is concentrated among disadvantaged populations: 18% of African Americans and 16% of people without a high school education have diabetes. Finally, diabetes is a condition that is well-suited to the study of self-monitoring, which appears to be a key factor in behavior change: glucose self-monitoring improves

outcomes among insulin-requiring diabetics and glucometers are covered by Medicaid in all states. A diabetes-specific trial can provide valuable insights that can be extrapolated to other diseases. Digital health applications extend to monitoring of weight, medication adherence, physical activity, blood pressure and other conditions. IMPaCT is adaptable and has been tested across many diseases. If we establish the effectiveness of a hybrid DFI/CHW intervention in this population, we will be able to generalize the intervention more broadly to improve health among low-income patients. We will test an innovative hybrid of two of the most promising and synergistic approaches for improving health among low income people in a way that is guided by behavioral and social science. This study will provide new knowledge of the pathways to behavior change and has the potential to improve the health of low-income individuals.

Primary outcome variable(s)

Primary outcome: Adherence rate (constructed by summing the number of days in the study period that the glucometer was used divided by the total number of days in study period.)

Secondary outcome variable(s)

The secondary outcome measure will be change in glycosylated hemoglobin from baseline to 24 weeks follow-up assessment.

Background

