
[name] was promoted to Clinical Research Coordinator and helped to transition the study into a clinical program embedded with the University of Pennsylvania Health System and the Corporal Michael J. Crescenz Veterans Affairs Medical Center. Additionally, [name] has worked as a clinical research coordinator on a behavioral science study in which he was responsible for reviewing literature and identifying useful survey instruments; developing study protocols; creating a research database and manual; meeting with clinic staff; supervising staff; and corresponding with the Institutional Review Board. [name] will work closely with [name] to oversee the day-to-day aspects of the study. Specifically, he will develop and maintain eligibility lists for recruitment purposes; coordinate and maintain IRB approval for the study; manage the tracking database of outcomes; supervise the work of the research assistant; assist with writing reports and correspondence with Commonwealth Fund; and coordinate quarterly meetings with all study team staff. The research assistant will have a minimum college education and will undergo a 1-week training which covers topics including survey interviewing, data entry, HIPPA and Human Subjects training. The research assistant will be responsible for interfacing with Way to Health platform, recruiting and enrolling patients, verbally administering the baseline and follow-up surveys, monitoring adherence and lottery, tracking laboratory results, and entering outcomes data.

Characteristics of the Study Population

Target population

Diabetes patients of low socioeconomic status living in high poverty zip codes of West/Southwest Philadelphia.

Subjects enrolled by Penn Researchers

150

Subjects enrolled by Collaborating Researchers

0

Accrual

We will enroll 150 patients (50 in each arm) from the Penn Rodebaugh Diabetes Center at the Perelman Center for Advanced Medicine.

Key inclusion criteria

Key inclusion criteria: We will enroll patients who meet the following eligibility criteria: 1) Penn Medicine patients diagnosed with diabetes mellitus (based on ICD-10CM codes from the year prior to study enrollment); 2) glycosylated hemoglobin 9% within the past 6 months; 3) requires insulin; 4) uninsured/publicly insured; 5) residents of high-poverty ZIP codes in West/Southwest Philadelphia; 6) have access to a cellphone with unlimited text message capabilities; 7) greater than or equal to 18 years of age.

Key exclusion criteria

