Key exclusion criteria: We will exclude patients who: 1) already have pumps that do continuous glucose monitoring; 2) were previously enrolled in the study; 3) are unwilling/unable to provide informed consent; 4) currently have a community health worker; 5) are in another study that asks participants to monitor their blood sugar.6) unable to speak and read comfortably in the English language

Vulnerable Populations

Children Form

Pregnant women (if the study procedures may affect the condition of the pregnant woman or fetus) Form

Fetuses and/or Neonates Form

Prisoners Form

Other

None of the above populations are included in the research study

The following documents are currently attached to this item:

There are no documents attached for this item.

Populations vulnerable to undue influence or coercion

The consent form is explicit about the absence of any consequences with respect to employees refusal to be involved in the protocol as a research participant altogether. The informed consent form is explicit about the absence of any consequences to refusing to participate in the study. We will be reimbursing participants up to \$200 over the course of the six month study period, as well as \$20 upon completion of an optional in depth qualitative interview. We feel this is a modest amount so that the compensation will not be unduly coercive even though we expect most of the participants to be low income and minority.

Participant recruitment

Please describe the plan to equitably identify and recruit a diverse group of participants that is reflective of the population under study. If this is a multicenter protocol, the recruitment plan should describe the local (Penn) site's plan. Describe: how potential participants may be identified (review of medical records, Slicer Dicer, DAC reports including referrals from physician offices and clinics); who may approach potential participants; methods to achieve sample diversity and inclusiveness; what information may be presented to or discussed with them; and the context and setting in which recruitment will happen.

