
the correct phone number using contact verification technology. Step Five: Labs 1. Walk the patient to the laboratory to have their blood drawn for HbA1c evaluation. 2. Provide the patient with a gift card and half page sheet with payment information Step Six: How to Use the Glucometer 1. Provide the patient with a glucometer if they don't already have one. 2. Review the user guide with the patient and answer any questions they may have about using their glucometer. 3. Reinforce/explain to the patient not to delete their glucose reading log from the glucometer because we will extract the log from the glucometer at subsequent visits. Abnormal Blood Glucose Safety Protocol: The study clinician will be notified by the way to health platform if participants glucose is either extremely low or high (60 or 400 mg/dL) and respond accordingly. The study clinician will contact these patients to address the issue. Step Seven: CHW escalation 1. The way to health platform will notify the study team of any individuals who have low adherence (no self-monitoring) or elevated glucose readings (300 mg/dL) for 30% of days over any 2 week period in the first 12 weeks of the study. These individuals will be assigned to receive ongoing CHW support for the duration of the 24-week study period 2. The study team should notify the CHW and send them the patients redcap ID. The CHW will follow up with the patient in 1-2 days. Step Eight: 3 Month Follow Up 1. One month prior, contact the patient to set a date/time for their 3 month follow up appointment. (If patients are unable to be reached, then we will send a letter to their home requesting that they contact us to set up a follow-up appointment.) 2. At the appointment, obtain the blood glucose log of readings from the patients glucometer. 3. Provide the patient with a gift card. Follow up visit is concluded. 4. The window to complete all 3-month follow-up procedures may be extended in cases where patients were prevented from completing visits within the original window due to COVID-19 restrictions. Step Nine: 6 Month Follow Up and Labs 1. One month prior, contact the patient to set a date/time for their 6 month follow up appointment. (If patients are unable to be reached, then we will send a letter to their home requesting that they contact us to set up a follow-up appointment.) 2. At the appointment, obtain the blood glucose log of readings from the patients glucometer. 3. Administer the follow up redcap survey 4. Walk the patient to the laboratory to have their blood drawn for HbA1c evaluation. 5. Provide the patient with a gift card. Follow up visit is concluded. 6. The window to complete all 6-month follow-up procedures may be extended in cases where patients were prevented from completing visits within the original window due to COVID-19 restrictions. Any Engage Study patients screened for recruitment into routine care community health worker programs at Penn Medicine will have their enrollment deferred until their study participation is complete. We will track all screened patients that are deferred because of Engage Study participation and contact them afterwards to offer enrollment into our routine care community health worker program. You may also be contacted during this study as a part of our quality review. If this happens you will just be asked a few questions about how the study has been going and your experiences with the steps listed above.

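### Exclusion 1 covers only pumps with continuous monitoring, so patients with a stand-alone sensor are eligible although the primary outcome can see only glucometer use

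*Combined protocol and SAP*

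**What the plan says.** Under Key exclusion criteria, item 1 removes patients who "already have pumps that do continuous glucose monitoring". The only other item that touches on monitoring removes those who "are in another study that asks participants to monitor their blood sugar"; it does not reach a sensor prescribed in routine care. Key inclusion criteria limit entry to a patient who "requires insulin".

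Under Primary outcome variable(s), and again in the Analysis Plan, adherence is built by "summing the number of days in the study period that the glucometer was used divided by the total number of days in study period". Step Six of Procedures names the data source: "we will extract the log from the glucometer at subsequent visits". The same step tells staff: "Provide the patient with a glucometer if they don't already have one".

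Step Seven of Procedures, and the description of the hybrid arm under Design, send to CHW support "any individuals who have low adherence (no self-monitoring) or elevated glucose readings" on 30% of days in any two-week period of the first 12 weeks. The Way to Health platform raises the alert.

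Nothing in the documents mentions a sensor worn without a pump, says whether sensor readings count as glucometer use or as self-monitoring, or plans to record sensor use.

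**The concern.** Eligibility is written around the pump, but the outcome is written around the meter. A patient whose sensor replaces finger-stick checks is monitoring glucose, yet contributes zero on every day without a meter reading. If such patients are spread evenly across arms, they pull both adherence rates towards zero and shrink the contrast the trial is powered to detect. In the hybrid arm the same patients could also be flagged for CHW support, the resource that the hybrid design is meant to target. Randomisation balances sensor use at baseline on average, but it does not remove this dilution and does not govern sensors started during follow-up.

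**Working it through.** **The plan's own figure.** Inputs from Sample size calculations: 40% adherence in usual care, 80% in hybrid, 80% power, Type I error 0.05 (taken as two-sided). The usual pooled-variance formula for two proportions gives 23 per arm without and 28 with continuity correction. The stated 28 is therefore the continuity-corrected figure. Inflation for 20% loss gives 28 × 1.20 = 33.6, rounded up to the stated 34, or 28/0.80 = 35. Neither figure is disputed. Planned enrolment of 50 per arm leaves 50 × 0.80 = 40 evaluable.

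**What one sensor user looks like.** A patient who never uses the meter scores 0 of 168 days. In a two-week window that patient has 14 of 14 days without a meter reading, against a trigger of 0.30 × 14 = 4.2 days.

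**Worst-case dilution.** The share c of sensor users is not in the documents. I assume 0 to 20%, the same in every arm, with every sensor user at zero meter days for all 24 weeks. Recorded rates become (1 − c) × the assumed rates. The secondary comparison uses the plan's 48% (DFI alone) and 80% (hybrid). With n = 40 per arm,

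power = Φ{[d − 1.96 √(2p̄(1 − p̄)/n)] / √[(p₁(1 − p₁) + p₂(1 − p₂))/n]},

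where d = p₂ − p₁ and p̄ is the mean of the two rates. The continuity-corrected version replaces d with d − 1/n.

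| c | Usual care v hybrid | Power, uncorrected/corrected | DFI v hybrid | Power, uncorrected/corrected |
|---|---|---|---|---|
| 0 | 40.0% v 80% | 0.968/0.946 | 48.0% v 80% | 0.861/0.799 |
| 5% | 38.0% v 76% | 0.945/0.912 | 45.6% v 76% | 0.807/0.735 |
| 10% | 36.0% v 72% | 0.913/0.869 | 43.2% v 72% | 0.750/0.670 |
| 20% | 32.0% v 64% | 0.830/0.764 | 38.4% v 64% | 0.634/0.544 |

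Because the plan's 28 is continuity-corrected, the second figure in each pair is the like-for-like one. On that basis the primary comparison stays above 80% at 10% and drops below it at 20%. The secondary comparison starts at the 80% line and falls below it at any appreciable share.

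**Escalations.** The Design section expects 25 of 50 hybrid patients to need CHW support. If every sensor user triggers and half of the rest do, the total is 0.5 × (50 − 50c) + 50c, so the net increase is 25c: 1.25, 2.5 and 5 patients at 5, 10 and 20%.

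**The case against.** The strongest reply is that the effect may be small or absent. The population is uninsured or publicly insured, the Objectives section describes glucometers as the device covered by Medicaid in every state, and nothing shows that any eligible patient wears a sensor. Staff provide a meter to anyone without one and teach its use, and the lottery pays for meter use in the first six weeks, so a sensor user who joins may well use the meter. This stands. It is why the figures above are a worst case and the share is an assumption. It does not close the gap, because the lottery ends at week 6 of 24 and is not offered in usual care.

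The trigger also refers to no self-monitoring rather than to no meter use. Escalating a sensor user assumes that the platform receives meter data only. That fits the data flow described, but it is not stated outright. The list is headed as key criteria, and the research assistant manual, which may hold further screening detail, is not among the pages available.

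Three stronger readings are tempting and not supported.

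- A reader might infer that the exclusion was written because continuous monitoring makes meter use uninformative. That is plausible, but the protocol gives no reason for it.
- A reader might infer bias against the hybrid arm, through CHWs prompting sensor use. The documents describe CHW work on socioeconomic barriers and coping with setbacks, not sensors, and contact begins only after a two-week trigger window. If 10% of hybrid patients started a sensor at week 6 and stopped using the meter, the arm's rate would be 0.9 × 80% + 0.1 × 80% × 6/24 = 74%. A start at week 12 gives 0.9 × 80% + 0.1 × 80% × 12/24 = 76%. Against 40%, power at 40 per arm is 88/83% and 92/88%. The bias could also run the other way: the lottery may draw meter readings from sensor users in the DFI and hybrid arms but not in usual care, widening that contrast without more actual monitoring.
- A reader might count every sensor user in the hybrid arm (2.5 to 10 of 50 at 5 to 20%) as an unnecessary escalation. About half would be expected to escalate anyway under the plan's own 50% assumption, and elevated readings are a separate trigger.

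**Conclusion.** The gap is real on the text: followed as written, the plan admits insulin-treated patients whose monitoring its primary outcome cannot register. At shares up to 20%, the worst case costs the primary comparison at most a fall in power from 97/95% to 83/76%. The comparison with DFI alone is more exposed, falling from 86/80% to 63/54%. Net extra escalations are about 1 to 5 of 50 at shares of 5 to 20%. These sizes rest on an assumed prevalence, on sensor users never using the meter, on equal shares across arms, and on 40 evaluable patients per arm. The escalation figure also assumes that the platform sees only meter data. If sensors are rare or users keep using the meter, the effect is close to nil. The direction of any bias cannot be settled from the documents, which is itself a reason to record sensor use. The change is worth making because it is cheap and protects the validity of the primary outcome, not because the trial is shown to be underpowered or biased.

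**What to change.** Reword exclusion 1 to current use of any continuous glucose monitor, with or without a pump. Record sensor use at baseline and at the existing 3- and 6-month visits, as yes/no with an approximate start date. For patients already enrolled, ask about baseline use at their next contact.

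Keep later starters, and any sensor users already enrolled, in the intention-to-treat analysis. Add a sensitivity analysis of the adherence comparison that either excludes patients with recorded sensor use or censors their days after the reported start. Where sensor use began after randomisation, both options condition on a post-randomisation event, so this should support the main analysis and not replace it. An analysis that credits sensor-wear days as monitoring days would need sensor downloads; the added question cannot supply them.

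The cost is a slightly smaller recruitment pool and one added question. Some follow-up dates had already passed when the COVID-19 compensation change was written, so the new wording affects only patients not yet enrolled. For the rest, the recording and the sensitivity analysis are what remain available.

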Participants interested in enrolling into the study will go through the following procedures: Step One: Consent and Goal-Setting 1. Explain the study to the patient using the consent form. Obtain two signed copies of the consent. 2. Use the IMPaCT goal card to help the patient choose a reasonable HbA1c goal to reach by the end of the six month study period. Step Two: 1. Administer the baseline redcap survey. Step Three: The Walk Tests (All parts of Step Three are optional and patients will be asked if they want to participate in this part of the study) 1. Take the patient to the walk test area. Ask the patient to sit at rest in a chair for a few minutes. During this time, explain the walk test to the patient: We would like you to participate in 2 or 3 walk tests. These tests can help us understand how you may react to this study, which asks you to monitor your blood glucose. We will ask you to complete a short walk test, 2 or 3 times. Before the test starts, check for contraindications, baseline oxygen saturation via pulse ox, pulse, and blood pressure. Patients should use their usual walking aids during the test(cane, walker, etc.). 3. Contraindications to administering the 1 minute walk test are: 1) resting heart rate of more than 120, 2) a systolic blood pressure of more than 180 mm Hg, 3) and a diastolic blood pressure of more than 100 mm Hg. If at the study visit, a patient cannot participate in the walk test because of a contraindication, the patient can complete all other aspects of the study. If the patient has any of these contraindications or a Sp02 less than 88%, this constitutes a clinical emergency and the principal investigator should be contacted immediately. 4. If no contraindications exist, set the timer to 1 minute. Assemble all necessary equipment (timer, clipboard, worksheet, cones) and move to the starting point. 5. Trial One (Practice Trial) a. After explaining the instructions, position the patient at the starting line. Say Start now, or whenever you are ready. b. Record the number of laps the patient walked from the tick marks on the worksheet. And record the additional distance covered (the distance in the final partial lap). Calculate the total distance walked. c. Congratulate the patient on their good effort and offer a drink of water. d. Give the patient a rest period. (Vitals will not be repeated before trials 2 and 3) 6. Trial Two (Performance Trial) a. After a rest period, ask participants to complete a second walk test with the goal of exceeding their prior performance (total distance walked) by 40%. (You should calculate the distance and just tell them that, not the percent). b. Conduct the walk test as above. c. After the walk test, tell the patient if they succeeded or failed at reaching their goal. 7. Trial Three (Outcomes Trial) a. Offer participants the choice of repeating their walk trial. "Now, I'd like to give you the option of doing another walk test to see if you can improve. Do you want to try again?" If they choose not to do Trial 3, leave their Trial 3 performance distance walked blank and move on. b. Repeat the walk test as above. c. After the completion of all the walk tests, thank the patient. Step Four: Set up Way to Health Account 1. Enter the patient into the way to health platform. 2. Test that they provided

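### Walk test: low oxygen saturation is called an emergency but is not a contraindication, so a patient with isolated low SpO2 meets the written start rule

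*Combined protocol and SAP*

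**What the plan says.** All the relevant text is in the combined protocol and SAP, Study Procedures, under Step Three (The Walk Tests).

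- **Who is exposed.** The step is voluntary: "All parts of Step Three are optional and patients will be asked if they want to participate in this part of the study".
- **Pre-test check.** "Before the test starts, check for contraindications, baseline oxygen saturation via pulse ox, pulse, and blood pressure".
- **Item 3, the list.** "Contraindications to administering the 1 minute walk test are: 1) resting heart rate of more than 120", then "2) a systolic blood pressure of more than 180 mm Hg, 3) and a diastolic blood pressure of more than 100 mm Hg". The list ends there.
- **Item 3, patients who cannot walk.** A patient kept from the test by a contraindication may still do everything else in the study.
- **Item 3, emergencies.** If the patient has "any of these contraindications or a Sp02 less than 88%, this constitutes a clinical emergency", the principal investigator is to be contacted at once.
- **Item 4, the start rule.** "If no contraindications exist, set the timer to 1 minute".

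The protocol also says that vital signs are not taken again before the second and third trials.

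**The concern.** Oxygen saturation is measured as part of the safety check and has a threshold serious enough to be called an emergency, yet that threshold is not connected to the decision to start. For pulse and blood pressure the protocol does not rely on the emergency label alone. It also lists them as contraindications, and item 4 acts on that list. SpO2 is the one measured value with an emergency threshold and no link to the start rule.

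What is at stake is participant safety in an exercise procedure, not inference. A hypoxaemic patient could be walked under a literal reading. No later measurement would catch the case, and the second trial asks the patient to beat the first distance by 40%. A smaller gap follows from the same omission: permission to continue with the rest of the study is tied to having a contraindication, so the text does not say what happens to a patient held back for low SpO2 alone.

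**Working it through.** The plan gives no figure to reproduce here. The check is a logical reading of items 3 and 4.

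**Inputs (Step Three)**

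- H: resting heart rate above 120 (item 3, contraindication 1)
- S: systolic pressure above 180 mm Hg (item 3, contraindication 2)
- D: diastolic pressure above 100 mm Hg (item 3, contraindication 3)
- O: SpO2 below 88% (item 3, emergency sentence only)

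**Rules as written**

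- Emergency (item 3) = H or S or D or O. The reference to any of the contraindications confirms that each one counts alone, and the word joining SpO2 to them places it outside the list.
- Start condition (item 4) = not H and not S and not D. O does not appear.

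**Enumeration.** Four yes/no checks give 2^4 = 16 combinations. The three listed items give 2^3 = 8, of which 1 has none present and 8 − 1 = 7 have at least one.

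| Any of H, S, D? | O? | Combinations | Emergency (item 3) | Start condition (item 4) |
|---|---|---|---|---|
| No | No | 1 | No | Met |
| No | Yes | 1 | **Yes** | **Met** |
| Yes | No | 7 | Yes | Not met |
| Yes | Yes | 7 | Yes | Not met |

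- Emergency: 1 + 7 + 7 = 15 combinations.
- Emergency and barred from starting: 7 + 7 = 14.
- Emergency and start condition met: 15 − 14 = 1, which is low SpO2 alone.

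**Example.** With SpO2 of 85% and heart rate, systolic and diastolic pressure all within limits, O is true and H, S and D are false. Item 3 calls this an emergency, while item 4's condition for starting the timer is satisfied.

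**After adding O to the list.** The start condition becomes not H, not S, not D and not O. One combination meets it (all four normal), and 0 of 16 are both an emergency and cleared to start.

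These counts describe the logic of the rule, not how often patients fall into each row. No other part of the document withholds the test for low SpO2.

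**The case against.** The strongest reply is that the conflict appears only if item 4 is read apart from item 3. The steps are sequential. Staff told to treat a patient as a clinical emergency and call the investigator at once would not then set a timer. The pre-test check also groups oxygen saturation with pulse and blood pressure, and item 3 gives low SpO2 the same emergency status as the listed items, so the intent to withhold the test is a fair inference. On this view the point is an editorial omission in an optional one-minute test that feeds no stated outcome.

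Most of that stands as a limit on practical risk. It does not remove the gap, because the stop has to be inferred for SpO2 while it is written out for pulse and blood pressure. It is also fair that the 16-combination count adds no evidence about likelihood; it only sets out the logic.

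A second reservation is that the Participant recruitment section mentions an attached research assistant manual that was not available for this review. The protocol cites it for the phone script. Whether it also covers the walk test is unknown, so the finding concerns the protocol text only.

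**Conclusion.** The concern holds: the start rule as written gives the wrong answer in one case, low SpO2 with normal pulse and pressures. It is a minor point, for the sponsor to consider.

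Only patients who opt into Step Three and show that one combination are affected. The documents give neither the opt-in rate nor the frequency of SpO2 below 88% in this population, so the number among the 150 planned participants cannot be derived and may be zero. The walk test is not among the stated primary or secondary outcomes or the hypotheses in the Analysis Plan, so the trial's results do not depend on it. The conclusion rests on a literal reading of items 3 and 4 and on no separate operating document supplying the missing stop rule.

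**What to change.** Add SpO2 less than 88% as contraindication 4 in item 3. Item 4 then bars the test without further editing, and a patient held back for low SpO2 is covered by the sentence allowing completion of the rest of the study.

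The alternative is to reword item 4 so that the timer is set only if no contraindications exist and SpO2 is 88% or higher. That closes the start rule but leaves the continuation question open, so the first option is better.

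Either change costs one phrase in the protocol. Sample size, visits and analysis are unaffected.
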